3. INTRODUCCIÓN

The impact of cancer in the western world and the growing number of people affected each year¹ means that new, increasingly effective and selective treatments are appearing relatively quickly. However, although these treatments are highly effective in killing tumour cells, they are not their only target. Molecules used in cancer treatments often affect healthy cells, causing side effects (nausea, diarrhoea, anaemia, immunosuppression, fatigue and hair loss). When antineoplastic therapies affect the sensory peripheral nervous system, they can cause peripheral polyneuropathy (NP or CIPN (Chemotherapy-Induced Peripheral Neuropathy)). The prevalence of this disease varies depending on the chemotherapy agent administered, affecting up to 80% of patients treated with taxanes (paclitaxel and/or docetaxel) or up to 95% of patients treated with oxyplatin². People with PN experience sensory discomfort, mainly in the extremities (numbness, dryness, tingling, burning, stinging, allodynia or hyperalgesia)³ which, over time, can

lead to the interruption of cancer treatment, with the risks that this entails. This condition often persists after the end of cancer treatment, which greatly affects the quality of life of those who suffer from it, as it can be uncomfortable when working, playing sports, carrying out household chores and even when socialising. In addition, the uncomfortable sensations can disturb sleep, which has an impact on mood. In general, people with NP caused by cancer treatments feel a great dissatisfaction with their skin.

Currently, there is no effective treatment for NP, and when the symptomatology is severe and limits patients' daily life, some doctors recommend taking antidepressants, such as duloxetine, or discontinuing chemotherapy treatment⁴. Although a number of clinical trials aimed at finding an effective treatment for NP have been conducted in recent years, none of them have proven to be effective. Therefore, understanding the mechanisms governing the development of PN and its treatment is a huge challenge in oncology as it is one of the main causes of chemotherapy withdrawal.

The Institute for Research, Development and Innovation in Health Biotechnology of the Miguel [name] University of Elche (IDIBE-UMH) has been studying the mechanisms that govern skin imbalances for many years. This knowledge has been transferred to Prospera Biotech, and has been used to develop a line of creams for sensitive skin (trade name Nocisens). The mixture of fatty acids, tocopherol and innovative cosmetic ingredients means that Nocisens has a dual action on the stratum corneum. On the one hand, it strengthens the skin's barrier function by preventing water loss, which helps to increase hydration and re-establish the skin's protective function and, on the other hand, it prevents the accumulation of reactive oxygen species in the cells, protecting the skin from their harmful effects. These two actions help Nocisens cosmetic cream to create a feeling of well-being and comfort for the skin.

However, in cosmetics, the degree of acceptance of a product is a key element for adherence to treatment. We have therefore developed two formulations derived from Nocisens, PB-011 and PB-012, with slightly different texture, composition and properties in order to adapt them to the needs of the sensitive skin characteristic of palmo-plantar neuropathy mediated by chemotherapeutics.

Given that PN induced by treatments with chemotherapy or chemotherapeutic agents fused to monoclonal antibodies (immunocytostatic) is characterised by skin imbalances that affect the quality of life of the people who suffer from it, a parallel, randomised, double-blind, masked study is proposed in patients who are about to begin oncological treatment to compare the

degree of acceptance of PB-011 and PB-012 cosmetic creams in this population. The study involves two populations: (i) the population where PB-011 cream will be tested; and, (ii) the population that will test PB-012 cream. The duration of the project will be 12 months, and participants will have to apply the cream once a day on their hands during the period of chemotherapy treatment. A sample size of 60 volunteers per population has been estimated to ensure statistical significance. As a relevant variable for the patients, the degree of skin satisfaction will be assessed every fortnight by means of a questionnaire only in the case of discomfort in the hands and/or feet.

4. JUSTIFICATION AND STUDY OBJECTIVES

The toxicity generated during chemotherapy treatments can usually produce skin discomfort or peripheral polyneuropathy. CIPN manifests itself above all in the extremities, mainly in the palmar and plantar regions, giving rise to uncomfortable sensations such as itching, numbness, tingling, pain or dryness, i.e. skin sensitivity. Currently, there is no specific treatment to combat this skin sensitivity and oncology specialists recommend keeping the skin hydrated through the use of cosmetic creams.

Taking into account that these sensations imply a deterioration in the quality of life of patients, our hypothesis is that cosmetic creams for sensitive skin with references PB011 and PB012 could improve comfort and the degree of satisfaction of cancer patients with CIPN. The reason for this hypothesis is that cosmetic creams contain ingredients that reinforce the barrier function of the epidermis and improve the hydration and appearance of the skin. The study has been designed to define which of the two creams produces greater satisfaction in patients.

5. TYPE OF STUDY AND DESIGN

5.1. Development phase

Multicenter, controlled, parallel, randomized, double-blind, masked study.

5.2. Randomization process

The assignment of cosmetic creams PB-011 or PB-012 to patients will be carried out by a simple randomization procedure, using random numbers.

5.3. Masking

To avoid bias, the study is proposed to be blind for patients and researchers and open to third parties (evaluators and those responsible for data analysis). To this end, a qualitative variable will be created, called product, of two degrees that will serve to mask the type of product used in each subject (PB-011/PB-012). The assignment of one product or another will be determined by the order of introduction in the study database. The definition of each degree of this qualitative variable will be in the possession of the main researcher and only when the study has finished and its results have been digitized, will it be transferred to those responsible for the statistical analysis. Both the data notebook and the databases or files used for statistical analysis will be dissociated from the identification data of the subjects under study.

Doctors and other study collaborators will have access to a list containing a fixed order of the products (A/B). For instance: product 1 is A, product 2 is B, product 3 is B... Investigators will assign a cream A/B to participants as they enter in the study (participant 1 will have A, 2 will have B, 3 will have B, etc). This list will be available physically and electronically.

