6.3. Expected number of subjects and justification

A total of 120 volunteers diagnosed with any type of cancer, in stages I-III, who are about to start or have received a maximum of 1 dose of chemotherapy treatment will be studied.

Two study populations are contemplated: (i) population that will receive the PB-011 cream; (ii) population that will receive the PB-012 cream. Both populations will apply the cream on their hands once a day. If sensory discomfort or, in the worst case, peripheral neuropathy appear during the chemotherapy treatment period, the application will be increased to twice daily on the affected areas (generally hands and feet).

The number of volunteers for the study is 60 for each population. This value is based on: (i) a difference of 2 points between both populations (PB-011 and PB-012), on a satisfaction scale of

0 to 10 points, with 0 being very dissatisfied and 10 very satisfied, or 2 points on the Von Frey scale; (ii) a variability (standard deviation) of 3 points in each population; (iii) a p-value of statistical significance <0.05 and, (iv) a probability of finding a statistically significant difference for the p-value <0.05 of 95%.

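### Simple randomisation from one shared A/B list leaves arm sizes and chemotherapy class to chance, and nobody is named to issue each list position across centres

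*Combined protocol and SAP*

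**What the plan says.** - **Design (5.1):** "Multicenter, controlled, parallel, randomized, double-blind, masked study". The text available for this review does not give the number of centres; part of section 2 was not in it.
- **Sequence (5.2):** assignment "will be carried out by a simple randomization procedure, using random numbers". There are no blocks and no strata.
- **Assignment (5.3), first statement:** "The assignment of one product or another will be determined by the order of introduction in the study database".
- **Assignment (5.3), second statement:** doctors and collaborators hold a fixed-order A/B list on paper and electronically, and "Investigators will assign a cream A/B to participants as they enter in the study". The example runs through participants 1, 2 and 3. The section does not say whether that count is kept across the study or within each centre, or who gives out the next line.
- **Inclusion (7.2):** the researchers notify the sponsor of each inclusion. The sponsor is not said to issue the assignment.
- **Target (6.3):** "The number of volunteers for the study is 60 for each population".
- **Agent (3 and 6.1):** "The prevalence of this disease varies depending on the chemotherapy agent administered", with ceilings of 80% for taxanes and 95% for the platinum agent named. Taxane, platinum and vincristine derivatives are all eligible.
- **Comparison (6 and 12):** section 6 compares the creams in patients who developed neuropathy. Section 12 will look at the impact of treatment, diagnosis, age and gender. It does not name centre and sets out no adjusted comparison of the creams.

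**The concern.** A doctor with a paper list but no live study-wide count cannot tell which line comes next. Two centres could then use the same line without either departing from the text. Patients at that position would share an assignment, and the sequence would no longer be the independent draws that 5.2 implies.

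Separately, even a single list used correctly neither fixes the arms at 60 each nor balances chemotherapy class. Class matters because, by section 3, it affects who develops neuropathy and therefore who enters the section 6 comparison. What is at stake is mainly the comparability of the arms and a clear operating rule. Power is a lesser matter.

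**Working it through.** **1. The plan's own figure.** Inputs from 6.3: difference 2, SD 3, significance 0.05 (taken as two-sided), power 95%.

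n per arm = 2 × (1.960 + 1.645)² × 3² / 2² = 58.5, so 59. The exact two-sample t-test needs 59.45, so 60. The stated 60 is reproduced, and power at 60/60 is 95.2%. A one-sided test would need 49, so two-sided is the matching reading.

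**2. One list, simple randomisation.** The size of arm A is Binomial(120, 0.5), with SD = √120 / 2 = 5.5.

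**3. The same list restarted at each centre.** With k equal centres (assumed), each uses lines 1 to 120/k. The size of arm A is then k × Binomial(120/k, 0.5), and its SD is √k × 5.5.

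| Centres restarting | SD of arm size | 95% range | Exactly 60/60 | 50/70 or worse |
|---|---|---|---|---|
| None (one list) | 5.5 | 49 to 71 | 7% | 8% |
| 2 | 7.7 | 44 to 76 | 10% | 25% |
| 4 | 11.0 | 40 to 80 | 14% | 36% |
| 6 | 13.4 | 36 to 84 | 18% | 50% |

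Restarting makes both the exact split and the extreme splits more likely, because arm sizes move in steps of k.

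**4. Power at unequal splits.** Two-sample t-test, all 120 analysed: 94.6% at 50/70, 94.5% at 49/71, 92.7% at 40/80 and 91.3% at 36/84. Averaged over the possible splits, power is 94.8%, 94.4% and 94.0% for 2, 4 and 6 restarting centres.

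**5. Chemotherapy class with one correct list.** For a class with share p, the 95% range of the difference in share between arms of 60 is ±1.96 × √(2p(1−p)/60).

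- p = 20% (assumed): ±14 percentage points.
- p = 50% (assumed): ±18 points; a difference of 15 points or more arises in about 12% of trials.

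If only 30 per arm reached the section 6 comparison (assumed), p = 50% would give ±1.96 × √(0.5/30) = ±25 points.

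**6. What a class imbalance could do to neuropathy incidence.** Taking the section 3 ceilings at face value, a 15-point difference in share shifts expected incidence by 0.15 × (95 − 80) = 2.25 points, or 0.0225 × 60 = 1.35 patients in an arm of 60. This is illustrative only: the figures are upper limits, none is given for vincristines, and severity is not covered.

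**The case against.** A reader might infer that 5.3 contradicts itself, that centres will restart at line 1, and that the 60/60 split and the balance by site and chemotherapy are lost as a result. The documents do not support this.

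- Both sentences in 5.3 refer to entry into the study and neither mentions a site. They can be read as one study-wide order. Restarting is possible but is not stated.
- A 60/60 split was never assured. One correct list delivers it in 7% of trials, and the 60 in 6.3 is a planning target.
- Reuse does not itself worsen site confounding. Equal-sized centres that all start at line 1 have the same A:B ratio.
- Balance by chemotherapy class is absent because 5.2 has no strata. List reuse is not the cause.
- Remote follow-up in 7.2 is allowed where needed. It is not presented as a feature of particular sites, so it does not show a site imbalance.

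It can also be said that simple randomisation is valid, that chance imbalance does not bias the comparison and is allowed for in the test, and that section 12 already means to look at several prognostic factors. All of this stands, and it limits the point to an improvement. It does not settle who issues each position. Nor does it justify leaving to chance a factor that the protocol itself links to neuropathy, when controlling it needs no extra patients.

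**Conclusion.** The point holds as a cheap improvement, not as an error that invalidates the design. Two gaps remain: no party is named to issue each list position once across centres, and simple randomisation controls neither arm size nor chemotherapy class.

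With one list, the arm-size range is 49 to 71 and the effect on power is negligible. With restarting, a 50/70 split or worse rises from 8% to between 25% and 50% for 2 to 6 centres, yet power is still about 93% at 40/80. The chance difference in class share is of the order of ±14 to ±18 points at 60 per arm.

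These sizes rest on assumed numbers of equal centres, assumed class shares of 20% to 50%, an unrestricted random list and all 120 patients analysed. The section 6 comparison would include fewer patients, so its chance differences would be larger and its power lower for reasons separate from this point.

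**What to change.** Replace 5.2 and the assignment sentences of 5.3 with one rule:

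- a computer-generated 1:1 allocation in permuted blocks of randomly varying size, held centrally;
- stratified study-wide by chemotherapy class (taxane / platinum / other);
- each position issued once, by a named central holder, when the site notifies the inclusion under 7.2;
- no list of upcoming assignments kept at sites.

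The last item also deals with investigators being able to see the coming sequence, which is a separate and more serious matter in 5.3.

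In section 12, include chemotherapy class in the PB-011 versus PB-012 comparison. Do not cross site with class: 4 centres (assumed) by 3 classes would give 12 strata averaging 120/12 = 10 patients, and incomplete blocks would erode the balance.

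The cost is a new list, a wording change and slightly more logistics at each inclusion, with no extra patients or visits. Balance within site is not guaranteed. The change has to be made before enrolment, because allocation cannot be repaired afterwards.

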6.1. Inclusion criteria

Patients must meet all the criteria that appear in this section to be included in the study.

- To be older than 18 years old.
- To be able to complete questionnaires.
- Give informed consent in writing.
- Being able to apply the product under test by oneself.
- To have been diagnosed with stage I-III primary cancer.
- To have received a maximum of one treatment session with chemotherapy (derivatives of taxane, platinum or vincristines).
- Eastern Cooperative Oncology Group (ECOG) performance status (PS) 0-2.
- Life expectancy greater than or equal to 6 months.

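### Site staff hold the fixed A/B allocation list and no step hides the next letter, so allocation is not concealed; section 5.3 is also inconsistent about who is blind

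*Combined protocol and SAP*

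**What the plan says.** Section 5.2 deals only with how the sequence is made: assignment "will be carried out by a simple randomization procedure, using random numbers".

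Section 5.3 then describes how the sequence is used, in two ways. First, "The assignment of one product or another will be determined by the order of introduction in the study database". Second, "Doctors and other study collaborators will have access to a list containing a fixed order of the products (A/B"), with a worked example of participants 1, 2 and 3 taking the first three letters. It adds "Investigators will assign a cream A/B to participants as they enter in the study" and "This list will be available physically and electronically".

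Section 7.2 requires eligibility and signed consent before a subject can enter, and has the researchers notify the sponsor of each inclusion. On the product it only refers back to the randomization procedure.

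On blinding, section 5.1 describes a "Multicenter, controlled, parallel, randomized, double-blind, masked study". Section 5.3 describes the study as "blind for patients and researchers and open to third parties (evaluators and those responsible for data analysis"). The same section leaves the meaning of the two codes with the main researcher and passes it to the analysts only after the study has ended and the results are digitized. Section 7.2 has the study collaborators of each centre carry out the end-of-treatment evaluations.

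**The concern.** Random numbers protect against selection bias only if the next assignment is unknown while someone decides whether, and when, a patient enters. A visible list removes that protection: entry can be brought forward, delayed or declined according to the letter.

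The entry criteria leave room for this. A patient qualifies before chemotherapy or shortly after it starts ("To have received a maximum of one treatment session with chemotherapy"), so timing is flexible. ECOG status and life expectancy in section 6.1 are matters of judgement.

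Steering favours one cream only if staff come to believe they know which letter is which. The design makes such a belief easier to form and to use. Two letters serve the whole trial, so one correct guess covers every participant. The introduction says the creams differ slightly in texture. Collaborators with access to the list also carry out evaluations, and recruitment is planned over 10 months.

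At stake is the trial's central comparison. Section 4 sets out to find which cream gives greater satisfaction, and section 2.3 says the better-accepted one will be marketed. Selection at entry cannot be undone reliably in the analysis.

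**Working it through.** **Inputs.** 120 participants, 60 per group (section 6.3); simple randomization (section 5.2), taken as probability 0.5 for each letter; list access and assignment rule (section 5.3).

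**The plan's own figure.** With a 2-point difference, SD 3, two-sided 5% and power 95%, n = 2 × (1.960 + 1.645)² × 3² / 2² = 58.5, so 59 per group. The t-test version gives 59.5, so 60. The stated 60 reproduces, and concealing the list would not change it.

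**How many assignments can be foreseen?**

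1. *Concealed.* Under simple randomization, past letters say nothing about the next. Correct guesses follow Bin(120, 0.5): mean 60 (50%), 95% range 49 to 71.
2. *List held and position known.* 120 of 120 (100%).
3. *List held, position known only to be one of k consecutive, equally likely entries.* The best guess is the commoner letter among the k. The expected share correct is E[max(X, k − X)] / k, with X ~ Bin(k, 0.5):

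| k (assumed) | share | of 120 |
|---|---|---|
| 1 | 1.00 | 120 |
| 2 | 0.75 | 90 |
| 3 | 0.75 | 90 |
| 5 | 0.69 | 82.5 |
| 10 | 0.62 | 74.8 |

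For example, k = 2: (¼ × 2 + ½ × 1 + ¼ × 2) / 2 = 0.75.

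Case 2 applies if each centre has its own list or can see all entries. Case 3 applies if one list is shared and a centre does not see the others' entries. Section 5.3 does not say which holds.

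**Opportunity to choose who gets which letter.** If the position is known and m eligible patients wait at one site, the next m letters are not all alike with probability 1 − 2 × 0.5^m: 0.50 for m = 2 and 0.75 for m = 3. How often this arises is unknown. Sections 6.3 and 6.4 imply 120 / 10 = 12 patients a month over all centres, and the readable text gives no number of centres.

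**Blinding statements side by side.**

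| Role | Called | But |
|---|---|---|
| Researchers | blind (5.3) | the main researcher holds the code (5.3) |
| Analysts | open (5.3) | receive the code only after study end and digitization (5.3) |
| Evaluators | open (5.3) | evaluations are done by centre collaborators, who have list access (7.2, 5.3), in a study called double-blind (5.1) |

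**The case against.** A reader might infer that every assignment is known before consent. The text does not go that far. Section 5.3 implies that the position is known when a cream is assigned; section 7.2 puts eligibility and consent before inclusion. In a multicentre trial with one shared list, a site that cannot see other centres' entries does not know for certain which letter comes next. This stands, and it is why the figure is a range. It does not restore concealment: even knowledge to within 10 entries beats guessing, and nothing in the order of steps in section 7.2 keeps the list from view beforehand.

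A reader might also infer that staff are unblinded. They are not by this route, because the list shows letters and not products. Each patient uses one cream and so does not compare textures, and the main variable is a patient questionnaire. These points lower the risk of biased reporting but do not bear on who is enrolled when.

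A third inference would be a stated bias or an inflated false-positive rate. The documents give no basis for its size. The SD of 3 in section 6.3 belongs to a 0 to 10 satisfaction scale, not to the DLQI named as the main variable.

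Finally, the wording about third parties being open may be loose translation, since some Spanish remains in the text. That is a reason to reword it. The general-information pages between sections 2.3 and 2.7 were not available, so any role descriptions there could not be checked; they would have to override the explicit text of section 5.3.

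**Conclusion.** The concern holds. Section 5.3 places a fixed sequence with the people who enrol, and no section that could be read hides the next letter until consent and eligibility are recorded. Foreseeability is 100% with per-centre lists or visible entries, and about 75% to 62% if a shared list's position is known to within 2 to 10 entries (assumed), against 50% if concealed. These figures measure opportunity; no amount of bias is claimed. The finding rests on reading a fixed order, used as participants enter, as a list held in advance, which is its natural meaning.

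The conflicting blinding statements are a secondary matter of wording, but they need settling in the same edit. Overall this is a cheap improvement that protects the main comparison.

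**What to change.** 1. Remove the list from the sites. Place the sequence and the A/B key with one named person who does not enrol, assess, administer questionnaires or analyse, and who is not the main researcher. Someone outside both the sites and the sponsor's commercial team is preferable, since the sponsor will market the better-accepted cream (section 2.3) and its team may help with questionnaires (section 7.2).
2. In section 5.3, replace the paragraph that begins "Doctors and other study collaborators will have access to a list containing a fixed order of the products (A/B"), including the instruction that investigators assign from the list, and the sentence "The assignment of one product or another will be determined by the order of introduction in the study database", with: *After signed consent and eligibility are recorded and the inclusion notice is sent, the holder releases the next assignment, preferably as a numbered pack.*
3. In the sentence on the code's meaning, name this holder in place of the main researcher. Keep only the clause that delays transfer to the analysts until the study has finished and results are digitized.
4. Delete the clause making third parties open, and state that patients, investigators, collaborators and evaluators stay blind until data lock.
5. If recruitment has begun, apply this to all later participants and record how many were assigned from the open list.

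Cost: a protocol amendment with ethics committee approval (section 11.4), a named holder, possible pack relabelling, and a short wait for release. The inclusion notice already exists in section 7.2. No extra patients or visits are needed.
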